## **6.7 FOLLOW-UP**

Participants with AE(s) that require hospitalization will be followed until resolution or stabilization of the AE. Participants will be followed until 60 days from date of catheter placement, initiation of off-study anticoagulation treatment, or death, whichever occurs first (see Section 6.9, Schedule of Events). 60 day follow-up can be performed by phone or chart review.

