Précis	
Peripherally inserted central catheters (PICCs) and indwelling subclavian vein central venous catheters (ie, "Mediports", "Port-a-Cath", or "ports") are frequently used in ambulatory cancer patients requiring chemotherapy, often remaining inserted for weeks to months. A major complication of central venous catheters is catheter-associated thrombosis (CAT), occurring in over 50% of patients. CAT can lead to substantial morbidity including pain, swelling, erythema, catheter occlusion, and the potential for thrombosis progression mandating anticoagulation. The anticoagulant treatment of CAT comes with inherent risks, including bleeding, increased healthcare costs surrounding the management and replacement of the catheter, and delays in cancer treatment. Previous studies have evaluated the role of traditional anticoagulants to prevent CAT but have failed to display favorable safety and efficacy profiles. Evaluation of contact activation factor (F) XII and FXI in device-associated thrombosis has demonstrated that inhibiting FXII or FXI reduces these thromboses in multiple animal models. FXII appears to be dispensable for hemostasis, as individuals with FXII deficiency have no bleeding diathesis, making it a promising target for antithrombotic therapy. Xisomab 3G3 is a first-in-class monoclonal antibody that binds to the A2 domain of FXI, preventing FXII-mediated FXI activation. Xisomab 3G3 has been shown to reduce device-associated thrombus formation in multiple preclinical models. In this phase 2 study, we will evaluate the safety and efficacy of a single dose of 2 mg/kg of xisomab 3G3 as prophylaxis against CAT in cancer patients having a catheter placed, as compared to historical controls. All participants in this trial will receive a single dose of xisomab 3G3 near the time of catheter placement. Study participants will undergo an upper extremity venous duplex ultrasound on day 14 (<math>\pm 4</math>) after catheter placement to evaluate the occurrence of CAT (symptomatic or asymptomatic). All anti-cancer therapy provided to the participant while on-study will be at the discretion of the treating physician and in accordance with institutional guidelines. Safety follow-up will continue for 60 days from the date of catheter insertion, or until resolution or stabilization of any clinically significant drug-related adverse event, after which they will be considered off-study.

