Primary Objectives	To evaluate the antithrombotic efficacy of prophylactic xisomab 3G3 treatment in cancer patients with a central venous catheter.

Secondary Objectives	To determine the safety and tolerability of prophylactic xisomab 3G3 treatment as measured by the incidence and severity of adverse events in cancer patients with a central venous catheter.
Exploratory Objective	Assessment of participant coagulation profiles, and the incidence of line occlusion requiring medical interventions to obtain patency.
Primary Endpoints	The number of participants with catheter-associated thrombosis, as defined by the total incidence of symptomatic and asymptomatic thrombosis, and thrombotic occlusion leading to device failure (start: administration of xisomab; end: Day 18)
Secondary Endpoints	The number of subjects with treatment-related adverse events (TRAEs) and treatment-emergent adverse events (TEAEs) will be summarized using frequency counts (start: time of consent, end: Day 60)
Exploratory Endpoints	Quantification of coagulation parameters and assessment of catheter occlusion (start: pre-dose, end: Day 18 [i.e., post-dose]): 
 
a. Activated partial thromboplastin time (aPTT)
 
b. Pharmacokinetic (PK) evaluation
 
c. Time to symptomatic catheter-associated thrombosis
 
d. Proportion of participants with a catheter occlusion requiring medical intervention
 

Number of Participants	
Duration of Therapy	1 day
Duration of Follow Up	60 days [post catheter placement]
Key Inclusion Criteria	
 
• Men and women, aged <math>\geq</math> 18 years and members of all races and ethnic groups will be included.
 
• Participants with any solid tumor malignancy that will undergo insertion of a central venous catheter (PICC or indwelling subclavian vein central venous catheter) as part of planned cancer-directed therapy per institutional standards
 
• Able to wait 1 day post-study drug infusion before receiving cancer-directed therapy.
 
• ECOG performance status <math>\leq</math> 2
 
• Expected life expectancy of <math>>6</math> months
 
• At time of enrollment, must have adequate platelet count (<math>>100 \times 10^9/L</math>)
 

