A total of 50 participants are planned for enrollment into this study. Eligibility will be confirmed prior to planned PICC line placement or indwelling central venous catheter placement. Eligible participants that are scheduled to have a catheter inserted as part of their planned anticancer therapy will be enrolled to receive xisomab 3G3. Within 48 hours of insertion of the PICC or indwelling catheter (i.e.  $\pm$  2 days) per institutional standards, participants will undergo IV placement and receive a single dose of xisomab 3G3. Standard procedures for catheter maintenance for sterility and patency will be performed each time the catheter is accessed for use including 10 to 20 ml of normal saline pulsatile flush before and after use and every 7 days in the outpatient setting. Two days after administration of xisomab 3G3 participants may proceed with planned, standard-of-care anticancer treatment in consultation with their treating physician and in accordance with institutional guidelines. The **primary objective** is to measure the efficacy of xisomab 3G3, as determined by the incidence of ultrasound-confirmed CAT (both symptomatic and asymptomatic) within 18 days after catheter insertion, compared to historical cancer controls. All participants will undergo duplex venous ultrasound and physical examination to evaluate symptomatic or asymptomatic CAT at 14 ( $\pm$  4) days after catheter placement. If participants develop symptoms suggestive of CAT such as arm pain, swelling, or erythema in the arm with the PICC, those participants will undergo standard-of-care workup with a unilateral extremity duplex venous ultrasound in the affected arm or leg. Participants that have confirmed CAT or other thrombosis found on imaging, per investigator assessment, will be treated at the discretion of their treating physician per institutional guidelines and standards of care. The duplex venous ultrasound assessment will include evaluation of disease history and physical exam to further assess possible thrombosis-associated symptoms. The **secondary objective** is to establish the safety and tolerability of xisomab 3G3 administered near the time of central line placement in patients that are diagnosed with and treated for solid tumors. All participants will be followed for 60 days (or until resolution/stabilization of any clinically significant drug-related adverse event) from time of catheter insertion to assess for AEs and medication use.

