## 7.5 ADVERSE EVENT ASSESSMENT AND FOLLOW-UP

The occurrence of an UP, AE or SAE may come to the attention of study personnel during study visits and interviews of a study participant presenting for medical care, or upon review by a study monitor. All AEs including local and systemic reactions not meeting the criteria for SAEs will be captured on the appropriate CRF, except for AEs definitely attributable to participant's planned anti-cancer treatment regimen. Information to be collected includes event description, time of onset, clinician's assessment of severity, seriousness, expectedness, relationship to study product (assessed only by those with the training and authority to make a diagnosis), and date of resolution/stabilization of the event. All AEs occurring while on study must be documented appropriately regardless of relationship. All AEs will be followed to adequate resolution.

Any medical condition that is present at the time that the participant is screened will be considered as baseline and not reported as an AE. However, if the study participant's condition deteriorates at any time during the study, it will be recorded as an AE.

Changes in the severity of an AE will be documented to allow an assessment of the duration of the event at each level of severity to be performed. AEs characterized as intermittent require documentation of onset and duration of each episode. At each study visit, the Investigator will inquire about the occurrence of AE/SAEs since the last visit. Events will be followed for outcome information until resolution or stabilization.

The Investigator will record all reportable events with start dates occurring any time after informed consent is obtained until 60 days post study agent dose or until the participant receives alternative anticoagulant therapy, whichever occurs first. Any SAE that occurs after treatment with alternative anticoagulant therapy will be reported only if the Investigator or current treating physician has assessed the SAE as related to the study treatment. Adverse events will be evaluated using the current version of the [CTCAE v5.0](#).

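### Sections 6.7 and 7.5 stop follow-up and event recording when an undefined kind of anticoagulation starts, while Section 2.1, the synopsis and footnote F run to Day 60; bleeding to Day 60 may be undercounted

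*Combined protocol and SAP*

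**What the plan says.** Two sections contain a cut-off.

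- Section 6.7: "Participants will be followed until 60 days from date of catheter placement, initiation of off-study anticoagulation treatment, or death, whichever occurs first".
- Section 7.5 records reportable events from consent "until 60 days post study agent dose or until the participant receives alternative anticoagulant therapy, whichever occurs first". An SAE arising "after treatment with alternative anticoagulant therapy will be reported only if the Investigator or current treating physician has assessed the SAE as related" (that is, attributed to xisomab 3G3).

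Three places contain none.

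- Section 2.1: "All participants will be followed for 60 days (or until resolution/stabilization of any clinically significant drug-related adverse event) from time of catheter insertion". The stated purpose is to assess AEs and medication use.
- Synopsis: "Safety follow-up will continue for 60 days from the date of catheter insertion", or longer for an unresolved drug-related event. The secondary endpoint there counts adverse events to Day 60.
- Section 6.9, footnote F: grade 3 and 4 SAEs, whether related or not, are reported up to 60 days after catheter placement, and AE evaluation includes major and clinically relevant non-major bleeding. The schedule marks AE and concomitant medication assessment at Day 60.

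On analysis, Section 8.2.3 reports the incidence of major or clinically relevant non-major bleeding with a 95% CI in the safety set. Section 8.1 defines that set as everyone dosed. Section 8.2.3 gives no rule for follow-up that ends early, and Section 8.4 imputes nothing.

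On anticoagulation, Section 5.3.3 lets standard-of-care anticoagulation start at any time alongside xisomab 3G3. It asks for antithrombotic use to be recorded only before the end of treatment visit. Footnote B takes new medications through that visit.

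**The concern.** Two coordinators following different sections would collect different events once a participant starts an anticoagulant. One would stop at that date apart from related SAEs; the other would continue to Day 60.

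The trigger may also be tied to the primary outcome. Every participant is scanned at Day 14 (±4), and Section 1.1 says that guidelines recommend anticoagulation once CAT is found. If CAT treatment counts as off-study or alternative anticoagulation, the people who leave bleeding ascertainment early are mainly those with CAT.

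Bleeding is the open safety question for this drug (Section 1.4.1). Section 1.3 reports that aPTT was still raised at day 14 and normal by day 28, so a cut-off near Day 14 could remove time in which some drug effect remains.

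**Working it through.** **The plan's own figure.** Section 8.3.1 gives 60% CAT without xisomab, a 20-point reduction, two-sided alpha 0.05, 80% power and 4% ineligible. By the one-sample normal approximation:

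n = [(1.96 × √(0.6 × 0.4) + 0.842 × √(0.4 × 0.6)) / 0.2]² = 47.1, so 48; 48 / 0.96 = 50.

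The planned 50 reproduces and is not in dispute. Nothing below changes it.

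**What is recorded after anticoagulation starts**

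| Event after the start | Section 7.5 | Footnote F | Section 2.1 and synopsis |
|---|---|---|---|
| SAE judged related | reported | reported if grade 3-4 | within follow-up |
| SAE judged unrelated | not reported | reported if grade 3-4 | within follow-up |
| Non-serious bleed | not recorded | bleeding is part of AE evaluation; the explicit 60-day sentence covers SAEs only | within follow-up |

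If footnote F governs, grade 3-4 serious bleeds are kept and the loss is mainly non-serious bleeding.

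**Direction.** Suppose CAT treatment triggers the cut-off, Section 7.5 is followed, and the target is all bleeding to Day 60. Participants who are cut off stay in the denominator. Their later non-serious bleeds, and serious bleeds judged unrelated, cannot enter the numerator. Bleeds before the cut-off still count. The proportion is therefore unchanged or too low.

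**Size per participant.** With 50 dosed, each participant whose first qualifying bleed is missed lowers the proportion by 1/50 = 2.0 points. As a hypothetical, recording 4 of 50 instead of 5 of 50 gives 8.0% (exact 95% CI 2.2-19.2%) instead of 10.0% (3.3-21.8%).

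**Lost observation (illustration only).** The assumed CAT rates are 60% (the design's untreated rate) and 60 − 20 = 40% (its target rate). Two further assumptions are not in the documents: 50-100% of participants with CAT start an anticoagulant, and they start at Day 14.

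- Participants cut off = 50 × CAT rate × uptake
- Person-days lost = participants cut off × (60 − 14), out of 50 × 60 = 3,000

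| CAT rate | Uptake | Cut off | Person-days lost |
|---|---|---|---|
| 40% | 50% | 10 | 460 (15.3%) |
| 40% | 100% | 20 | 920 (30.7%) |
| 60% | 50% | 15 | 690 (23.0%) |
| 60% | 100% | 30 | 1,380 (46.0%) |

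Moving the start across the scan window gives 10 × 42 = 420 (14.0%, Day 18) at the low end and 30 × 50 = 1,500 (50.0%, Day 10) at the high end. Zero uptake gives zero. These figures measure lost observation, not bias.

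**Medication record.** The scan takes place at the end of treatment visit, before the provider sees the participant. An anticoagulant started at that visit falls within footnote B. Later starts fall outside both footnote B and Section 5.3.3, although Section 2.1 and the Day-60 schedule mark cover medication to Day 60.

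**The case against.** The strongest objection concerns the trigger. Because Section 5.3.3 allows standard-of-care anticoagulation alongside xisomab 3G3, treatment of CAT may be neither off-study nor alternative. The loss concentrated in CAT cases would then not arise. This stands: that part of the point is conditional, and the undefined terms are part of the problem.

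Next, the cut-off may be deliberate. Section 1.1 cites major hemorrhage up to 4.9% on CAT anticoagulation, with bleeding approaching 25% in some series, so later bleeds would mix two drugs' effects. This is a legitimate target, but no section states it, and Section 8.2.3 reports a plain proportion over all dosed participants.

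The consequence is also bounded. Related SAEs are still reported under Section 7.5, the bleeding analysis is descriptive with no decision threshold, and the primary endpoint is untouched. All of this stands.

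Three stronger readings are tempting but not supported.

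- A reader might infer that Section 7.5 contradicts itself, since it also says "All AEs occurring while on study must be documented appropriately regardless of relationship", and that Section 3.7 confirms this by not listing anticoagulation among the off-study criteria. But the list in Section 3.7 is open, and it includes completing follow-up and investigator's discretion. A participant whose follow-up ends under Section 6.7 can therefore be off study, and the sentence is then consistent with the cut-off.
- The Day-60 endpoint in Section 2.2.2 is tied to the end of follow-up, which could be read through Section 6.7. It is not relied on here.
- Section 8.3.1 might be taken to forecast 40-60% CAT in this trial. It gives an untreated rate and a difference to detect. Treated participants may have fewer events, so 40% is not a floor.

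**Conclusion.** The conflict between Sections 6.7 and 7.5 and Section 2.1, the synopsis and footnote F is plain in the current text and should be fixed. The undercount is conditional: it requires that CAT treatment, or some other common reason for anticoagulation, triggers the cut-off, that Section 7.5 is the text followed, and that all bleeding to Day 60 is the target. Under those conditions the error runs only downward, at 2.0 points per participant missed. The number missed cannot be derived from the documents and may be zero. The 10-30 participants and 15-46% of person-days rest on assumed CAT rates, uptake and timing; fewer CAT events or lower uptake gives less. The medication gap is confined to anticoagulants started after the end of treatment visit.

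**What to change.** 1. Reconcile Sections 6.7 and 7.5 with Section 2.1, the synopsis and footnote F, so that AEs, and bleeding as defined in Section 6.1.9.1, are recorded to Day 60 for every dosed participant whether or not an anticoagulant is started. Section 6.7 already allows phone or chart review for this contact.
2. Define off-study and alternative anticoagulation, and state whether treatment of CAT is included.
3. Reconcile footnote B and the recording sentence in Section 5.3.3 with Section 2.1 and the schedule, so that anticoagulant start dates are captured to Day 60.
4. In Section 8.2.3, report Day-60 bleeding overall, with a descriptive split before and after anticoagulation starts. If bleeding before other anticoagulation is the intended target, say so in Sections 2.2.2 and 8.2.3 and use a method that accounts for the cut-off in place of a raw Day-60 proportion.

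The cost is a minor amendment and a few more data fields. The downside is that bleeds after anticoagulation are harder to attribute to the study drug; the split shows this but does not resolve it.

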## **6.8 UNSCHEDULED VISITS**

Unscheduled study visits may occur at any time if medically warranted. Any assessments performed (e.g., laboratory or clinical assessments) at those visits should be recorded in (e)CRF.

## 6.9 SCHEDULE OF EVENTS

Visit Days*	Screening**	On-Study Treatment	End of Treatment Visit Day 14 ( $\pm 4$ days)	Follow-Up Day 60 ( $\pm 4$ days)
	Days -28 to -3	Day 1		
Informed consent	X			
Inclusion/exclusion criteria	X			
Catheter placement A		X		
Xisomab 3G3		X		
Medical history	X			
Medication history	X			
Physical Examination C	X	X G	X	
Radiographic Imaging		Per investigator's discretion, as clinically indicated		
Ultrasound D			X	
Hematology	X			
Biochemistry	X			
Coagulation	X		X	
Pregnancy test E	X			
AE assessment and Conmeds B,F	X	X	X	X
Research blood draw/Assessment for Immunogenicity H	X	X	X	
Electrocardiogram I	X	As clinically indicated		

\* Ideally the clinic visit and all the study requirements should be performed as indicated.

\*\* Enrolled participants will receive a single fixed dose of xisomab 3G3 (2 mg/kg) through a peripheral IV or the inserted catheter within 48 hours of catheter placement (i.e.  $\pm 2$  days). If Xisomab 3G3 is administered prior to D1 catheter placement, eligibility must be confirmed prior to study drug administration.

A Placement of the catheter in participants will be performed according to institutional guidelines. Ultrasound may be used to guide the placement of the catheter, and may include use of local anesthetic.

B For concomitant medications – enter new medications started during the trial through the end of treatment visit.

C All physical exams will include assessing vital signs, weight and ECOG performance status.

D Per institutional standards, study participants will be evaluated for CAT via planned ultrasound 14  $\pm 4$  days after catheter insertion. Additional ultrasound evaluations may occur at any time during the study based on treating physician and PI discretion; however, only ultrasounds performed within 18 days from catheter placement will be included when computing CAT incidence. Ultrasound to occur as part of EOT, prior to provider visit.

E For women of reproductive potential, a serum pregnancy test should be performed within 3 days prior to first dose of trial treatment. Serum pregnancy test should be performed by the local study site laboratory per institutional guidelines, and repeated if required.

Visit Days*	Screening**	On-Study Treatment	End of Treatment Visit Day 14 ( $\pm 4$ days)	Follow-Up Day 60 ( $\pm 4$ days)
	Days -28 to -3	Day 1		
			F AEs and laboratory safety measurements will be graded per NCI CTCAE version 5.0. All AEs, whether gradable by CTCAE or not, will also be evaluated for seriousness. Report grade 3 and 4 hematological and non-hematological SAEs (related and unrelated to trial treatment) occurring up until 60 days after catheter placement. AE evaluation includes assessment of major and clinically-relevant non-major bleeding per Section 6.1.9.1.	
			G Study visit to occur within 24hrs or day of single dose of study treatment. If screening visit occurs within 24hrs of study treatment administration, D1 provider visit does not need to be repeated.	
			H Blood will be collected and batched on day 14 for Immunogenicity assessment. The Day 1 blood draw should be obtained any time prior to study drug administration.	
			I Electrocardiogram will be obtained at screening and as clinically indicated.	

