## 2.2.2 SECONDARY OBJECTIVES AND ENDPOINTS

Objective	Endpoint	Start	End
To evaluate the safety and tolerability of xisomab 3G3 in cancer patients with a PICC or indwelling catheter	
 
1. Incidence of major and clinically-relevant bleeding [refer to Section 6.1.9.1]
 
2. Incidence of xisomab 3G3-associated toxicities [per CTCAE v5.0]
 
	Administration of xisomab 3G3 (Day 1 ± 2 days)	End of follow-up (Day 60)

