## 2.2.3 EXPLORATORY OBJECTIVE AND ENDPOINT

Objective	Endpoint	Start	End
Assessment of drug exposure and catheter occlusions leading to medical intervention	
Quantification of coagulation profile:
 
 
1. aPTT
 
2. PK evaluation
 
3. Time to thrombosis (i.e., symptomatic CAT)
 
4. Proportion of participants with a catheter occlusion requiring medical intervention (i.e., local administration of tPA)
 
	pre-xisomab 3G3 administration	Day 18

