### 5.3.2 TRANSFUSIONS OF PLATELETS AND RED BLOOD CELLS (RBC)

Blood, plasma, platelet or red blood cell transfusions are permitted as medically necessary per institutional guidelines. The decision for platelet or red blood cell transfusions should be done in collaboration with study investigator and participant's treating physician. The occurrence of any transfusion occurring prior to end of treatment visit on Day 14 ( $\pm$  4 days) should be recorded in (e)CRF. Abnormal, clinically significant bleeding may be managed at the discretion of the physician. Antifibrinolytic agents such as tranexamic acid may be used in the event of major bleeding events, and bleeding refractory to this may be managed with recombinant factor VIIa (Novo7) or prothrombin complex concentrates, at the discretion of the treating physician and in consultation with study PI.

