### 5.3.3 ANTI-PLATELET AGENTS AND ANTICOAGULANTS

Anti-platelet agents and anticoagulants are permitted only as medically necessary, in case of new thrombosis, and managed per institutional guidelines. Standard of care anticoagulation may be started at any time in conjunction with xisomab 3G3 if deemed warranted by the treating physician. Anti-platelet agents and/or anticoagulants may not be given prior to administration of xisomab 3G3. The decision regarding use of antithrombotics should be done in collaboration with study investigator and participant's treating physician. Participants should be carefully monitored for bleeding risks. The use of any anti-platelet agents or anticoagulants occurring prior to end of treatment visit should be recorded in (e)CRF.

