## **6.6 END OF TREATMENT VISIT**

An end of treatment visit should occur on Day 14 ( $\pm 4$  days) after catheter placement and include assessments listed in Section 6.9, Schedule of Events.

If a participant does not reach the end of treatment due to transition to hospice or death, an end of treatment visit will not be conducted.

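### Medication and transfusion recording rules end at the end of treatment visit, which conflicts with section 2.1 and falls short of the Day 18 occlusion and Day 60 bleeding windows

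*Combined protocol and SAP*

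**What the plan says.** Three places end recording at the end of treatment visit:

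- Section 6.9, footnote B, on concomitant medications: "enter new medications started during the trial through the end of treatment visit".
- Section 5.3.3: "The use of any anti-platelet agents or anticoagulants occurring prior to end of treatment visit should be recorded in (e)CRF".
- Section 5.3.2 asks for this in the CRF: "The occurrence of any transfusion occurring prior to end of treatment visit on Day 14" (±4 days).

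Section 6.6 fixes the timing: "An end of treatment visit should occur on Day 14", again ±4 days, so the visit may fall anywhere from Day 10 to Day 18.

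Other parts of the protocol look further ahead. Section 2.1 follows all participants for 60 days "from time of catheter insertion to assess for AEs and medication use". Section 2.2.3 lists as an exploratory endpoint the "Proportion of participants with a catheter occlusion requiring medical intervention (i.e., local administration of tPA"), with a window ending on Day 18. Section 2.2.2 lists "Incidence of major and clinically-relevant bleeding" as a secondary endpoint, with a window ending on Day 60.

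Two further rules bear on anticoagulants. Section 6.7 ends follow-up when off-study anticoagulation begins, if that comes before Day 60 or death. Section 7.5 ends general event recording when alternative anticoagulant therapy is received. After that, only SAEs assessed as related to study treatment are reported.

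**The concern.** A CRF built from footnote B, 5.3.2 and 5.3.3 would stop collecting exposures that the endpoints need.

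For occlusion, a medication defines the event. If the medication log closes at a visit that may be on Day 10, a tPA-treated occlusion on Day 12 counts for a participant whose visit is on Day 14. It may not count for one whose visit is on Day 10. The estimated proportion then depends partly on clinic scheduling.

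For bleeding, anti-platelet agents and transfusions are relevant context to Day 60, and neither has a recording instruction after the visit. The start date of an anticoagulant matters under either reading of the protocol. If 6.7 and 7.5 govern, it is the date on which bleeding follow-up is cut off. If the 60-day follow-up in 2.1 governs, it is needed to interpret each later bleed. Section 5.3.3 does not require it once the visit has passed, and 8.2.3 mentions neither censoring nor anticoagulant exposure.

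**Working it through.** The plan gives no figure of its own on this point, and the planned sample size of 50 does not depend on it. The check is date arithmetic on the visit window, then a comparison of the sections.

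**Inputs.** End of treatment visit on Day v, with v from 10 to 18 (6.6). Occlusion window to Day 18 (2.2.3). Bleeding window to Day 60 (2.2.2). Day 1 is catheter insertion (3.5).

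**Days outside the recording rules.** Occlusion: 18 − v. Bleeding: 60 − v.

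| Visit day v | Occlusion: 18 − v | Share of 18 days | Bleeding: 60 − v |
|---|---|---|---|
| 10 | 8 | 44% | 50 |
| 14 | 4 | 22% | 46 |
| 18 | 0 | 0% | 42 |

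The last column is the span in which anti-platelet and transfusion use has no recording instruction, for a participant still in follow-up. It does not measure lost anticoagulant data (see the objection).

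**How many occlusions might this be?** The documents give no occlusion rate, so this part is an assumption with a range. Take an 18-day rate r of 5%, 10% or 15%, a constant hazard h = −ln(1 − r)/18, and 48 evaluable participants (50 × 0.96). The expected number after a visit on Day v is 48 × [exp(−hv) − exp(−18h)]. For r = 10%, h = 0.00585. With v = 10 this gives 48 × (0.9431 − 0.9000) = 2.1.

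| Assumed r | Expected in 18 days | After visit, all on Day 10 | After visit, all on Day 14 |
|---|---|---|---|
| 5% | 2.4 | 1.1 | 0.5 |
| 10% | 4.8 | 2.1 | 1.0 |
| 15% | 7.2 | 3.1 | 1.5 |

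These are occlusions that fall after the visit. They are not all lost, because other records may catch some.

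**Anticoagulants.** Footnote B includes the visit itself, whereas 5.3.3 covers only use before it. The ultrasound is done at that visit, ahead of the provider visit (6.1.8), so an anticoagulant started there because of the scan is inside footnote B but outside 5.3.3. One started the next day is outside both. Yet 6.7 and 7.5 make that start the end of follow-up and of general event recording, so the date has to be known.

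**The case against.** **Other sources may fill the gap.** Nothing says the occlusion endpoint is derived from the medication log, and the CRF is not among the documents. Adverse events are recorded to 60 days, subject to the anticoagulation stop (7.5), and assessments at unscheduled visits go into the CRF (6.8). This stands in part: some later occlusions will be caught. But 5.4 allows tPA flushes as standard care for occlusion, so a site need not report one as an adverse event, and the schedule has no separate occlusion assessment.

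**The endpoint is exploratory, and Day 10 is the extreme.** Both are true. The gap is 0 to 8 days, and a share of days is not a share of events.

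**Stronger readings that the documents do not support.**

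- A reader might infer that later bleeds on xisomab alone could not be told apart from bleeds on treatment anticoagulation, so that the safety conclusion fails. Sections 6.7 and 7.5 point elsewhere: once anticoagulation starts, most later bleeds are not collected at all, and the start has to be ascertained because it ends follow-up.
- A reader might take 46 of 60 days (77%) as the share of anticoagulant data lost. Under 6.7 those who start leave follow-up, and those who do not start have nothing to record.
- A reader might count about 19 of 48 participants (0.40 × 48, at the design's target rate) as unrecorded anticoagulant courses. That is the expected number with catheter-associated thrombosis. Treatment is discretionary (2.1), and a course started by or at the visit is inside footnote B.
- A reader might think a missing transfusion entry changes how a bleed is classified. Transfusion is not a criterion in 6.1.9.1; the record would only corroborate.
- A reader might cite the Day 60 mark on the schedule row for adverse events and concomitant medications as a contradiction. Footnote B qualifies that row, and its adverse-event half explains the mark. The clear conflict is with 2.1.
- The synopsis adds "thrombotic occlusion leading to device failure (start: administration of xisomab; end: Day 18") to the primary endpoint, so a reader might extend the point to it. The documents do not define that component by tPA, and 8.2.2 analyses ultrasound-detected thrombosis.

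**Conclusion.** The point holds as an internal conflict, with one definite gap and several smaller ones. The recording rules in footnote B, 5.3.2 and 5.3.3 are narrower than 2.1 and shorter than the endpoint windows. Which text governs is unresolved, so it cannot be said that the data will go unrecorded, only that a site following the specific rules need not record them.

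For occlusion, 0 to 8 of the 18 days (4 for a Day 14 visit) lie outside medication recording, and ascertainment varies with visit date. Under the assumed rates of 5% to 15%, about 0.5 to 1.5 occlusions would fall after the visit if every visit were on Day 14, and about 1.1 to 3.1 if every visit were on Day 10. For bleeding, the gaps are anti-platelet and transfusion use after the visit, and the anticoagulant start date that 6.7 and 7.5 depend on.

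An exploratory endpoint and the context for a secondary safety endpoint are affected. The sample size and the analysis set out in 8.2.2 are not. The change should be made because data not collected prospectively may not be recoverable.

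**What to change.** 1. Reconcile footnote B, 5.3.2 and 5.3.3 with 2.1, 6.7 and 7.5, so that one recording period is stated for each type of exposure.
2. Record catheter-directed tPA, with its date, through Day 18 for every participant. This includes anyone whose follow-up would otherwise end earlier under 6.7.
3. Record anticoagulant, anti-platelet and transfusion use, with dates, through Day 60. Section 6.7 already provides a Day 60 contact by phone or chart review.
4. In 8.2.3, report bleeding by anticoagulant exposure only if 6.7 and 7.5 are reconciled so that bleeds after anticoagulant start are collected. Otherwise such a table would be nearly empty after the start date, and 8.2.3 should state that bleeding follow-up is censored there.

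The cost is protocol wording and a few more CRF fields. No extra visit is needed, and neither the sample size nor treatment changes.
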